#### 11.3 Withdrawal

Approximately 150 subjects will be enrolled to ensure that a minimum of 135 evaluable subjects complete the study. If a subject withdraws from the study, he or she will not be replaced.

A subject will be withdrawn (i.e., dropouts) from the study for any of the following reasons:

- Lost to follow-up;
- Deemed ineligible (following screening) at Visit 1;
- Subject request/Withdrawal of Informed Consent: A subject may withdraw consent any time without negative implication to the subject. The withdrawal will be documented in source documents and the Case Report Form (CRF);
- Non-compliant in the judgment of the Investigator;
- Adverse event that requires intervention in region injected;
- Termination of study by the Sponsor;
- The PI believes that for safety reasons (e.g., AE, concurrent illness) it is in the best interests of the subject to be withdrawn from study participation;
- The subject's attending physician requests that the subject be withdrawn from the study;
- The PI or the Sponsor, for any reason, stops the study or stops the subject's participation in the study;

Protocol deviations will not lead to automatic withdrawal unless they indicate a significant risk to the subject's safety. All major protocol deviations must be discussed promptly with the Medical Monitor.

A subject may be withdrawn from the study, in consultation with the Medical Monitor, for any of the following reasons:

- Lack of compliance to study procedures;
- A major protocol deviation or violation;
- Poor visit attendance.

If a subject decides to withdraw from the study, or should the PI decide to withdraw the subject, the PI (or designate) will complete and report the observations up to the time of withdrawal.

Unless withdrawn during a study visit, subjects who are withdrawn from the study will be requested to come in to complete an Early Termination Visit as soon as reasonably possible so that a complete evaluation at the time of the subject's withdrawal should be made. Additionally, subjects who withdraw from the study will be requested to allow continued safety monitoring, either via telephone interviews or clinic visits, whichever is more appropriate.

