#### **11.4** Termination of Study

#### **11.4.1** Termination by Sponsor

The Sponsor may terminate the study at any time for any of the following reasons:

- Failure to enroll subjects
- Inaccurate or incomplete data
- Unsafe or unethical practices
- Questionable safety of the study drug
- Administrative decision

The Investigator/Institution will be promptly informed by the Sponsor in writing of termination of the study and reason(s) for termination. The Investigator must inform the IRB promptly and provide a detailed written explanation of the termination and must also promptly notify all participating subjects of the termination of the study within 24 hours and assure that all appropriate therapy and follow-up for subjects is provided.

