#### **11.4.2** Termination by Investigator

If the Investigator terminates the study prematurely, the Investigator will:

- Provide the IRB and the Sponsor with a written statement describing why the study was terminated prematurely. Prompt compliance with this requirement is essential so that the Sponsor may comply with regulatory obligations.
- Notify all participating subjects of the termination within 24 hours and ensure that all appropriate therapy and follow-up for subjects is provided.
- Return all CRFs, and related study materials to the Sponsor.

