7.5.2. Per-Protocol Population	
7.5.3. Safety Population	
7.6. Sample Size Considerations	
7.7. General Considerations	
APPENDIX A: STATISTICAL TABLES	

Version 1.1 31-May-2023 Confidential Page 6/58

ABBREVIATIONS

ADDREVIATI	
AE	Adverse Event
BLA	Biologic License Application
BP	Blood Pressure
CFR	U. S. Code of Federal Regulations
CI	Confidence Interval
CRA	Clinical Research Associate
CRO	Clinical Research Organization
ECG	Electrocardiogram
ET	Early Termination
eCRF	electronic Case Report Form
FDA	Food and Drug Administration
GCP	Good Clinical Practices
GAIS	Global Aesthetic Improvement Scale
GLS	Glabellar Line Scale (0=none, 1=mild, 2=moderate, 3=severe)
HIPAA	Health Insurance Portability and Accountability Act
ICF	Informed Consent Form
ICH	International Conference on Harmonization
IND	Investigational New Drug
IP	Investigational Product
IRB	Institutional Review Board
ITT	Intent-to-Treat
PI	Principal Investigator
PP	Per protocol
SAE	Serious Adverse Event
SAFT	Safety
SAP	Statistical Analysis Plan
SMMP	Safety and Medical Monitoring Plan
SOC	System Organ Class
SSS	Subject Satisfaction Scale
TRAE	Treatment Related Adverse Event
UADR	Unanticipated Adverse Drug Reaction
ULN	Upper Limit of Normal
UPT	Urine Pregnancy Test
US	United States

Confidential Page 7/58

evolus™

This Statistical Analysis Plan (SAP) gives a comprehensive and detailed description of statistical techniques to be used for study EVOLUS-CLIN201. The purpose of this SAP is to ensure the credibility of the study findings by pre-specifying the statistical approaches for the analysis of study data prior to database lock. This SAP provides additional details concerning the statistical analyses outlined in the protocol. Whenever differences exist in descriptions or explanations provided in the protocol and SAP, the SAP prevails.

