7.7. General Considerations

Data will be listed by subject number. Data will be summarized by treatment and study visit, where applicable. For categorical parameters, the number and percentage of subjects/observations in each category will be presented; percentages will be based on the number of subjects in the relevant analysis population in each treatment group. For continuous parameters, descriptive statistics will include n (number of subjects or observations), mean, standard deviation, median, and range. A full description of the statistical methods planned for this study will be provided in the Statistical Analysis Plan (SAP). All programs for data output and analyses will be written in SAS version 9.4 or higher (SAS Institute, Inc., Cary, NC).

Missing Values: For the mITT analysis of primary, secondary, tertiary, and exploratory duration of effectiveness endpoints, in the case of a missed visit, subjects will be considered to have returned to Baseline if they are confirmed to have returned to Baseline at the next non-missed visit. Subjects will be considered to have to have returned to Baseline if they fail to attend 2 consecutive visits or drop out of the study. For missing observations for exploratory endpoints other than duration of effect data will be analyzed as observed without imputation.

Discontinuation and Drop-Outs: Dropouts will not be replaced. Subject disposition will summarize the number of subjects who were randomized and who discontinued from the study (including reasons for discontinuation).

Interim Analysis: An interim analysis will be conducted when >90% of subjects have completed Visit 8 (Day 120) to evaluate response to exposure (efficacy, duration) and adverse events. For assessment of the primary effectiveness endpoint, 95% CIs will be presented but statistical analyses will not be conducted and a statistical penalty for the final analysis will not be employed. While data by treatment group will be presented, individual subjects will not be unblinded.

Poolability of Investigative Sites: Data from all investigative sites will be pooled based on the assumption of clinical comparability: the same protocol will be used for all sites, all sites will be monitored for protocol compliance, and the same data collection instrument and methodology will be used across all sites.

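### If the study or a site is stopped, the dropout rule scores every subject still in effect as having returned to Baseline

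*Protocol*

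**What the plan says.** Protocol 11.3 opens its list of mandatory withdrawals with subjects being "withdrawn (i.e., dropouts) from the study for any of the following reasons". Two of the listed reasons concern the study and not the subject. One is "Termination of study by the Sponsor". The other begins "The PI or the Sponsor, for any reason, stops the study or stops" and goes on to cover an individual subject's participation as well.

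Protocol 11.4.1 states that "The Sponsor may terminate the study at any time for any of the following reasons", and an administrative decision is one of the reasons it lists. Protocol 11.4.2 provides for early termination by an Investigator: "If the Investigator terminates the study prematurely, the Investigator will" carry out certain notifications.

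The analysis rule is under Missing Values in SAP 7.7, and Protocol 12.8 repeats it: "Subjects will be considered to have to have returned to Baseline if they fail to attend 2 consecutive visits or drop out of the study". It applies to the mITT analysis of all duration endpoints. The SAP's opening paragraph, before section 1.1, adds: "Whenever differences exist in descriptions or explanations provided in the protocol and SAP, the SAP prevails". The SAP does not define dropout itself.

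**The concern.** SAP 2.3 defines the primary endpoint so that treatment counts as effective for as long as GLS has not gone back to its Baseline severity. A subject whose GLS is still better than Baseline on the day the Sponsor closes the study has not met that event. Under the combined wording the subject is nonetheless scored as an event. A better-than-Baseline GLS at the Early Termination visit would not prevent this, because the rule looks only at whether the subject dropped out.

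Scoring a subject's own dropout as failure can be defended as conservative. A stop imposed on the whole study or site is normally unrelated to the subject's GLS course and would ordinarily be censored.

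At stake are the hazard ratio and the Kaplan-Meier median for what SAP 7.1 calls the most influential outcome. The timing also matters. Results by treatment group are presented at the interim analysis, so a rule changed after a stop could look data-driven.

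**Working it through.** **1. Does any text rescue the rule?**

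- Protocol 11.2 treats a subject as complete after an event that rules out further participation. It does not mention a study stop.
- SAP Table 14.3.1.1 has a row for censored subjects, and SAP 7.6 assumes 10% annual censoring. Neither says that a study stop is censored.
- Table 14.1.2 has no category for a study or site stop.

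Nothing displaces the literal reading.

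**2. The plan's own figure.** Inputs from SAP 7.6: 50 per arm, exponential times, 4-month reference median, hazard ratio (HR) 0.47, one-sided alpha 0.025, 80% power, 10% annual censoring.

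- Events needed (Schoenfeld): 4(1.96 + 0.84)² / (ln 0.47)², which gives 56. Freedman's formula gives 61.
- Expected events with 12 months of follow-up: 72.1. Power is 0.893 (Schoenfeld) or 0.865 (Freedman), not 0.80.
- The stated 80% is matched at about 7 months of follow-up (Schoenfeld, 0.802) or 8 months (Freedman, 0.796).

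SAP 7.6 gives no follow-up or accrual, and the point here does not depend on this mismatch.

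**3. Who is still in effect at a stop.** The monthly hazard is ln 2 / 4 = 0.1733 for 20U and 0.47 × 0.1733 = 0.0814 for 40U. The number still in effect at month t is 50·exp(−hazard × t). At month 6 this is 50·exp(−1.040) = 17.7 for 20U and 50·exp(−0.489) = 30.7 for 40U. The 40U share of the two arms is 30.7 / (17.7 + 30.7) = 63%. Across three arms, assuming onabotulinumtoxinA behaves like prabotulinumtoxinA 20U, it is 30.7 / (2 × 17.7 + 30.7) = 46%.

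| Follow-up at stop | 20U | 40U | 40U share, two arms | 40U share, three arms |
|---|---|---|---|---|
| Month 4 | 25.0 | 36.1 | 59% | 42% |
| Month 6 | 17.7 | 30.7 | 63% | 46% |
| Month 9 | 10.5 | 24.0 | 70% | 53% |
| Month 11 | 7.4 | 20.4 | 73% | 58% |

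The three-arm share passes 50% only after about 7.5 months. At HR 0.7 the two-arm share is 55-64% over the same months and the three-arm share stays below half. At HR 1 the shares are 50% and 33%.

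**4. Effect on the result.** Trials were simulated with these inputs, monthly detection, a 12-month cap and an unadjusted Cox model with Efron ties. The documents give no accrual length or stop date, so these are assumptions. Accrual ranged from 0 to 6 months. The stop came 6, 9 or 12 months after first entry, or when the last subject reached Day 120-180. No other dropout was included. The plan also does not say on which day an imputed dropout event falls.

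| Scenario, true HR 0.47 | Stop censored | Stop counted as event |
|---|---|---|
| Whole study: HR | 0.46-0.49 | 0.61-0.79 |
| Whole study: power | 63-85% | 20-68% |
| One of five sites: HR | 0.47-0.48 | 0.52-0.55 |
| One of five sites: 40U median | 270 days | 180-210 days |

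As an example, take 3 months of accrual and a stop at month 6. About 36 of 50 subjects on 40U and 25 of 50 on prabotulinumtoxinA 20U become imputed events. The HR reads 0.79 instead of 0.47. The 40U median reads 4 months, where it would usually not be estimable; the true value is 4 / 0.47 = 8.5 months. In the single-site case about 4-6 subjects on 20U and 6-8 on 40U are affected.

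At HR 1 the imputed events are equal by arm and the one-sided error stays at about 2-3%.

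**The case against.** The strongest reply is that 11.3 is an operational withdrawal list and not an analysis definition. It includes subjects found ineligible at Visit 1, who are screen failures and could never be in the mITT population. SAP 7.7 does not cite it, and the heading that follows names discontinuation and drop-outs as two terms. On that view the SAP has merely left a term undefined. This stands as to where the repair belongs. It does not remove the problem, because 11.3 is the only place where either document equates a class of subjects with dropouts, and no text censors a stop.

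The reply also says that the matter is hypothetical, that the trial is declared not powered for inference, and that the bias runs against the sponsor's product. All three are true and limit the weight of the power figures. The HR and median would still be reported. If every subject stops at the same follow-up time (month 6), log-rank power moves only from 76% to 70%, but the Cox HR still goes from 0.47 to 0.71.

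Nor are all stops uninformative. Protocol 11.4.1 also lists doubts about drug safety, unsafe or unethical practices, and poor data. The second 11.3 item also covers stopping one subject's participation, which may relate to effect. Protocol 11.4.2 does not say that an Investigator's termination is confined to one site; that is the natural reading, but an inference.

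**Conclusion.** The point holds as a conflict between the dropout rule and the endpoint definition, conditional on a stop. With HR 0.47 and the accrual and stop dates assumed above, a whole-study stop moves the HR to roughly 0.6-0.8, and closure of one of five sites moves it to about 0.52-0.55.

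A reader might infer that the false events fall mostly in the 40U arm. The documents do not say so. It is true against prabotulinumtoxinA 20U only if 40U lasts longer, and across the three arms 40U is a minority for a stop before about 7.5 months. A reader might also infer a risk of a false positive. None appears: the bias is toward HR 1, and equal arms show no imbalance and no type I inflation. Neither document plans or reports a stop.

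**What to change.** Add to SAP 7.7: *For the duration-of-effect analyses, subjects whose follow-up ends only because the whole study or their site is stopped are not dropouts; they are censored at their last in-person Investigator GLS assessment (for subject-rated endpoints, at the last corresponding subject assessment).* In-person is specified because Protocol Appendix A keeps remote Investigator GLS out of the primary analysis. Stops of an individual subject's participation stay under the existing dropout rule.

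Because the SAP takes precedence, this sentence is enough for the analysis. Rewriting 11.3 now would be a protocol amendment with full review under Protocol 3.1, so it can be aligned at the next amendment. Table 14.1.2 can report the stop in its existing row for other reasons.

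The cost is one sentence and no new data. The small downside is that censoring may not be fully uninformative after a stop for safety or data quality. Reporting the existing event rule as a sensitivity analysis covers that case.

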#### **11.4** Termination of Study

#### **11.4.1** Termination by Sponsor

The Sponsor may terminate the study at any time for any of the following reasons:

- Failure to enroll subjects
- Inaccurate or incomplete data
- Unsafe or unethical practices
- Questionable safety of the study drug
- Administrative decision

The Investigator/Institution will be promptly informed by the Sponsor in writing of termination of the study and reason(s) for termination. The Investigator must inform the IRB promptly and provide a detailed written explanation of the termination and must also promptly notify all participating subjects of the termination of the study within 24 hours and assure that all appropriate therapy and follow-up for subjects is provided.

#### **11.4.2** Termination by Investigator

If the Investigator terminates the study prematurely, the Investigator will:

- Provide the IRB and the Sponsor with a written statement describing why the study was terminated prematurely. Prompt compliance with this requirement is essential so that the Sponsor may comply with regulatory obligations.
- Notify all participating subjects of the termination within 24 hours and ensure that all appropriate therapy and follow-up for subjects is provided.
- Return all CRFs, and related study materials to the Sponsor.

# **12 STATISTICAL METHODS**

#### 12.1 Primary Endpoint

The primary effectiveness endpoint will be duration of effect, defined as the number of days from Treatment Day (Baseline) to the day that GLS severity (Investigator assessment) at maximum frown returns to the Baseline value. Although the trial is not powered for inferential analysis, this will be the most influential outcome in the overall assessment of the effectiveness of prabotulinumtoxinA 40 Units, compared to prabotulinumtoxinA 20 Units, in treating moderate to severe glabellar lines. Analysis will be performed using the modified Intent-To-Treat (mITT) population.

Duration of effect will be described by Kaplan-Meier curves and the respective median times with associated 2-sided 95% confidence interval (CI) for each treatment group. Statistical analyses of treatment group differences will be done using Cox proportional hazards regression with time to return to Baseline as the dependent variable, treatment group as the independent variable, and age, gender, and Baseline GLS score (Investigator assessment) at maximum frown as covariates.

Statistical significance will be established at the 0.025 level with one-sided hypothesis testing.

#### 12.2 Secondary Endpoints

Secondary effectiveness endpoints will be used to provide additional evidence of prabotulinumtoxinA 40 Units superiority to prabotulinumtoxinA 20 Units. As duration of effect outcomes, secondary effectiveness endpoints will be assessed as described above for the primary endpoint. The mITT population will be used for summaries and comparisons. Secondary endpoints, in order of importance, will be:

- 1. Duration of effect, defined as the number of days from Treatment Day (Baseline) to the day that GLS severity (subject assessment) at maximum frown returns to the Baseline value.
- 2. Duration of effect in GAIS responders (score of 2 or 1) as assessed by Investigator.
- 3. Duration of effect in GAIS responders (score of 2 or 1) as assessed by subject.
- 4. Duration of effect in SSS responders (score of 2 or 1) as assessed by subjects.

#### **12.3** Tertiary Endpoints

Tertiary effectiveness endpoints will be used to compare prabotulinumtoxinA 40 Units to onabotulinumtoxinA 20 Units, as well prabotulinumtoxinA 20 Units to onabotulinumtoxinA 20 Units. As duration of effect outcomes, tertiary effectiveness endpoints will be assessed as described above for the primary endpoint. The mITT population will be used for summaries and comparisons. Tertiary endpoints, in order of importance, will be:

- 1. Duration of effect, defined as the number of days from Treatment Day (Baseline) to the day that GLS severity (Investigator assessment) at maximum frown returns to the Baseline value.
- 2. Duration of effect, defined as the number of days from Treatment Day (Baseline) to the day that GLS severity (subject assessment) at maximum frown returns to the Baseline value.
- 3. Duration of effect in GAIS responders (score of 2 or 1) as assessed by Investigator.
- 4. Duration of effect in GAIS responders (score of 2 or 1) as assessed by subject.
- 5. Duration of effect in SSS responders (score of 2 or 1) as assessed by subjects.

#### 12.4 Exploratory Effectiveness Endpoints

Exploratory effectiveness endpoints will be evaluated for signals of effectiveness to explore whether any should be elevated in importance for subsequent trials. These endpoints will be assessed using either logistic regression (for binary endpoints) or survival analysis-type methods as described above. Comparisons will be made between all treatment groups. Chi-square tests of association or Fisher's exact tests will be used to compare treatment group differences in proportion of subjects returning to Baseline at each time point in the study. Exploratory endpoints will be:

- 1. GLS score of 0 or 1 (maximum frown) as assessed by Investigator and subject at each visit.
- 2. GAIS response (score of 2 or 1) as assessed by Investigator and subject at each visit.
- 3. SSS response (score of 2 or 1) as assessed by subjects at each visit.
- 4. 1-point or greater, 2-point or greater, and 3-point or greater improvement on the GLS (maximum frown) as assessed by Investigator at each visit.
- 5. 1-point or greater, 2-point or greater, and 3-point or greater improvement on the GLS (maximum frown) as assessed by subject at each visit.
- 6. Duration of effect in responders with a 1-point or greater, 2-point or greater, and 3-point or greater improvement on the GLS (maximum frown) as assessed by Investigator at each visit.
- 7. Duration of effect in responders with a 1-point or greater, 2-point or greater, and 3-point or greater improvement on the GLS (maximum frown) as assessed subject at each visit.
- Buration of effect in GLS responders (responder = ≥1-point improvement on GLS at Day 30) as assessed by Investigator.
- Duration of effect in GLS responders (responder = ≥1-point improvement on GLS at Day 30) as assessed by subject.
- 10. Onset of effect as assessed by subjects through the 7-Day Subject Diary.

#### 12.5 Safety Endpoints

Safety endpoints will include incidence of treatment-emergent and treatment-related AEs and changes from Baseline in ECG parameters, safety laboratory parameters, physical exams, and vital signs. The SAFT Population will be used for descriptive summaries of the safety endpoints.

#### 12.5.1 Adverse Events (AEs)

AEs will be coded to system organ class (SOC) and preferred term (PT) using the Medical Dictionary for Regulatory Activities (MedDRA). The number and percentage (incidence) of subjects reporting an AE and the number of AEs will be summarized.

A treatment-emergent AE will be defined as AEs that started at or after the first injection.

The following AE incidence tables will be provided for treatment-emergent AEs:

- All AEs by SOC and PT
- Related AEs by SOC and PT
- All AEs by PT sorted by decreasing frequency among all subjects
- Related AEs by PT sorted by decreasing frequency among all subjects
- All SAEs by seriousness criterion
- Related SAEs by seriousness criterion

- All SAEs by SOC and PT
- Related SAEs by SOC and PT

Treatment-related AEs will be defined as possibly, probably, or definitely related. Two-sided Wilson 95% confidence intervals will be calculated for the overall incidence of AEs and SAEs.

